3.7.3.2 Analysis

The following dose regimes will be analysed for DoR and DoCR: “100 / 20”, “40 / 15”.

The following will be presented by dosing regimen.

- The number of participants included in the analysis, those with event and those who are censored.
- The estimate of the median, 25th and 75th percentiles for tumour response durations (months).
- The duration of response rate at 3, 6, 9, 12 and 15 months.

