A visit window of ± 2 days is permitted for the Day 0 visit (the dose of radioactivity will be based on the actual administration date). Weekly assessments should occur within a window of ± 2 days. Visits occurring at 3 week intervals will have a window of ± 3 days. During the treatment and follow-up periods, a window of ± 7 days for visits is acceptable. For PET/CT and CT evaluation a window of ± 7 days is acceptable for treatment and follow-up periods.

The investigator may perform more frequent examinations than shown in Table 6-8 if clinically needed. Data from such additional examinations are also to be recorded in the eCRF.

All safety samples/assessments at baseline are to be obtained before dosing. Blood samples for haematology must be taken, analysed and evaluated within 24 hours prior to Betalutin administration.

Table 6-5 Schedule of Assessments – Part A, Phase I

Test Type	Screening	Treatment period								Follow-up period					
	Pre-study within 4 weeks before rituximab infusion	D-14 W2 prior dosing	D-1/D0 Day -1/ Dosing Day ¹² before adm	D0 Dosing Day ¹³ after adm	D1 (24±6) hours	D2 (48±12) hours	D4 (96±24) hours	D7 (168±24) hours	W 2, 3, 5, 6, 7, 9, 10, 11 Local GP (±3 days)	Month 1, 2 (±3 days)	Month 3 (±2weeks)	Month 6 (±2weeks)	Month 9 (±2 weeks)	Month 12 (±2 weeks)	W52-5 years ¹ Hospital visit every 6 months (±3 weeks)
Hospital visit	X	X	X	X	X	X	X	X		2X	X	X	X	X	8X
Informed consent	X														
Demographics	X														
Medical History	X														
Rituximab administration		X													
Lilotomab administration			X ²												
Betalutin administration				X											
Concomitant medication/therapy	X		X	X	X	X	X	X		X	X				
Cancer related treatment only excl. analgesics												X	X	X	8X
Physical examination ⁸	X		X	X ⁶	X	X	X	X		X	X	X	X	X	8X
Vital signs incl. temp	X		X	X ⁶	X	X	X	X		X	X				
Pregnancy test (if applicable)	X														
ECG			X												
WHO PS	X		X				X			X	X	X	X	X	8X
Hematology	X		X		X	X	X	X	8X	X	X	X	X	X	8X
Serum biochemistry ⁷	X		X		X	X	X	X	8X	X	X	X	X	X	8X
Lymphocyte subset	X										X	X	X	X	
Hepatitis B test	X														
Immunoglobulin levels	X										X	X	X	X	
HAMA level	X							X		X(W4 only)	X	X		X	
CD37 expression	X ³										(X ⁵)	(X ⁵)	(X ⁵)	(X ⁵)	(X ⁵)
Bone marrow biopsy	X ¹¹										X ¹⁰	X ¹⁰			
Radioactivity in blood ⁴			X	3-5X	X	X	X	X	X (week 2 and 3 only)						
Gamma Camera Images, only few pts. ⁴				X	X		X	X							
SPECT/CT ⁴							X ¹³								
Urine sampling ⁴					X										

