4) When patient is biopsied at relapse CD37 expression should be assessed. CD37 biopsy at relaps is optional

5) Bone marrow biopsy required for confirmation of CR if patient had bone marrow infiltration at baseline, otherwise it is optional

6) Blood samples weekly until platelet counts ≥ 100 x 10⁹/L and neutrophil counts (ANC) ≥ 1.5 x 10⁹/L after nadir values 7) A visit window of +/- 2 days is permitted for Day 0 visit. GP= general practitioner or local hospital

Note: during the COVID-19 pandemic, it may be necessary to perform certain study procedures remotely. All assessments must be recorded in the eCRF

Table 6-8 Schedule of Assessments - Part B, FL Phase IIb "PARADIGME" and Part C, Pharmacokinetic Cohort Phase IIa

Test type	Screening	Treatment period								Follow-up period				
	Pre-study (Within 4 weeks before 1st rituximab dose)	D-14 W2 prior to dosing	D-1/D0 Day -1 or Dosing Day before adm (±2 day)	D0 Dosing Day after adm	D+7 W1 (±2 day)	D+21 W3 (±2 days)	D+28 W4 (±2 days)	W5, 6,7,9,10,11 ⁶ (±2 days)	Month 2 W8 (±3 days)	Month 3 W12 (±7 days)	Month 6 W26 (±7 days)	Month 9 W39 (±7 days)	Month 12 W52 (±7 days)	W53-5 years ¹ Hospital visit every 6 months (±7 days)
Hospital visit	X	X	X	X			X		X	X	X	X	X	8X
Informed consent	X													
Demographics	X													
Medical History	X													
FL (Part B) or iNHL (Part C) disease stage and previous treatment	X													
Rituximab administration		X												
Lilotomab administration ²				X ²										
Betalutin administration				X										
Cancer related treatment only excl analgesics											(X) ⁷	(X) ⁷	(X) ⁷	(X) ⁷
Concomitant medication/therapy	X	X	X	X			X		X	X				
Physical examination	X		X				X		X	X	X	X	X	8X
Vital signs including temperature, weight and height	X		X	X ^p			X		X	X	X	X	X	8X
Pregnancy test (if applicable)	X ¹³		X				X			X	X	X	X	
WHO (ECOG) Performance Status	X		X				X		X	X	X	X	X	8X
Haematology	X	X	X		X	X	X	X	X	X	X	X	X	8X
Serum biochemistry	X		X		X	X	X	X	X	X	X	X	X	8X
Coagulation parameters (PT/INR & PTT)	X									X				
Lymphocyte subset	X									X	X	X	X	
Viral serology ¹²	X													
Immunoglobulin levels	X									X	X	X	X	
HAMA test	X													
Immunogenicity (ADA)			X ⁹		X		X			X	X		X	X ⁸
CD37 expression in tumour tissue	X ³													(X) ⁴

Test type	Screening	Treatment period								Follow-up period				
	Pre-study	D-14	D-1/D0	D0	D+7	D+21	D+28		Month 2	Month 3	Month 6	Month 9	Month 12	W53-5 years ¹

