14.1.2.2 Interim Analysis – Part B Randomised

Note - The interim analysis was introduced in Protocol Version 11 and amended in protocol Version 13.

Once approximately 50 patients have been treated (approximately 25 per dose regimen), an interim analysis will be performed on the ORR based on IRC assessment for the study. There is no statistical test of hypothesis in the interim analysis.

In line with its charter, the SRC will review the results of the interim analysis and provide a recommendation to the Sponsor to continue or terminate treatment arms or to perform other modifications based on the totality of safety, efficacy, and other available data (e.g. immunogenicity data). The final decision lies with the sponsor.

The SRC will take into account the following guidelines: if ORR \geq 40% in each treatment regimen, the study may complete its targeted enrolment of up to 130 patients, around 65 per arm. If ORR < 40% in either regimen then the regimen with ORR <40% may be terminated. If both regimens have ORR <40%, the study may be terminated for futility or modified. There regimen(s) with ORR \geq 40% will proceed to enrol the remaining patients, up to 130 total.

To facilitate decision to keep or drop treatment arms based on ORR rates, the boundary of 40% ORR is non-binding and for guidance only.

The primary efficacy endpoint is overall tumour response rate according to the IRC. Scans will be performed at baseline, 3, 6, 9, 12, 18, 24, 36, 48 and 60 months after Betalutin injection for all patients to assess tumour response (see [Section 14.1.7](#)).

Response rates will be presented as a percentage of the Intent-to-Treat (ITT) population with the exact 95% confidence interval (Clopper-Pearson).

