3.7.4.1.1 Analysis

The following will be presented by dosing regimen.

- The number of participants included in the analysis, those with event and those who are censored.
- The estimate of the median, 25th and 75th percentiles for progression free survival time
- The progression free survival rate at 3, 6, 9, 12 and 15 months.

The corresponding KM plot of the probability of being progression free against time will also be presented.

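### DoR/DoCR landmark times, and some PFS ones, are set without regard to the scan dates, so several reported rates carry forward an earlier scan and overstate durability

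*SAP*

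**What the plan says.** **Landmarks.** SAP 3.7.3.2 covers DoR and DoCR and lists "The duration of response rate at 3, 6, 9, 12 and 15 months", beside event and censoring counts, median and quartiles. SAP 3.7.4.1.1 lists "The progression free survival rate at 3, 6, 9, 12 and 15 months" and adds a Kaplan-Meier plot. Section 3.7.3.2 lists no plot for DoR.

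**Event dates.** Under SAP 3.7.3.1 and 3.7.4.1, progression takes the date of the first assessment that shows PD, and deaths keep their own date. Time in months is (difference in days + 1) × 12/365.25. The clock starts at first documented response for DoR and at Betalutin administration for PFS.

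**Scans.** Protocol 14.1.2.2 states: "Scans will be performed at baseline, 3, 6, 9, 12, 18, 24, 36, 48 and 60 months after Betalutin injection for all patients". Table 6-8 ties the first four to W12, W26, W39 and W52, with two in year 2 and one a year after that. Protocol 6.3 adds: "For PET/CT and CT evaluation a window of ± 7 days is acceptable for treatment and follow-up periods".

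No SAP rule aligns landmarks with scans, and no interval-censored or similar sensitivity analysis is planned. The month windows in SAP 3.3 apply to laboratory outputs only.

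**The concern.** A progression found on a scan enters the Kaplan-Meier estimate on the scan date. If a landmark falls just before a scan, the rate at that landmark describes the previous scan, and everything that happened in the interval is still counted as response. A landmark placed after the scan window would count it.

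The SAP's round-month times appear to have been chosen without checking this. DoR is most exposed, because its clock starts at a scan and its landmarks then depend on the gap between two scans. OS is not derived under this SAP, so DoR, DoCR and PFS are its only durability results. A reader could take a carried-forward status for observed durability.

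**Working it through.** The documents state no landmark rate, so there is no figure of the plan's own to reproduce. The inputs are the scan days (84, 182, 273 and 364), the ±7-day window and the SAP's month formula. Month 18 is taken as day 548 (assumption).

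**1. DoR, response first seen at W12**

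| Next scan | Gap (days) | Months of DoR | Landmark | Progressions dated after landmark |
|---|---|---|---|---|
| W26 | 98 | 99 × 12/365.25 = 3.25 | 3 | 88% |
| W39 | 189 | 190 × 12/365.25 = 6.24 | 6 | 88% |
| W52 | 280 | 281 × 12/365.25 = 9.23 | 9 | 88% |
| Month 18 | 464 | 465 × 12/365.25 = 15.28 | 15 | 91% |

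The last column takes each scan as uniform over 15 whole days, independently. Three months is 91.31 days, so the gap must be at most 90 days to count by then. The two windows must together shorten 98 days by at least 8, which 28 of 15 × 15 = 225 pairs do (12%). The 6- and 9-month cases also need 8 days. Fifteen months is 456.56 days, so 464 must shorten by at least 9: 21/225 = 9%.

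At nominal dates no later scan precedes 3 months. No scan lies between 9.23 and 15.28 months, so the 12- and 15-month rates both rest on the W52 scan.

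**2. DoR, response first seen at W26**

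The gaps to W39, W52 and Month 18 are 91, 182 and 366 days, or 3.02, 6.01 and 12.06 months.
- At 3 and 6 months a shortening of 1 day suffices: 105/225 = 47% by the landmark, 53% after it.
- At 12 months (365.25 days) a shortening of 2 days is needed: 91/225 = 40% by the landmark, 60% after it.
- At 9 months the rate carries forward the 6.01-month scan.

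**3. PFS**

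| Scan | Months | Landmark | Scan on or before landmark |
|---|---|---|---|
| W12 | 85 × 12/365.25 = 2.79 | 3 | 14/15 = 93% |
| W26 | 183 × 12/365.25 = 6.01 | 6 | 7/15 = 47% |
| W39 | 274 × 12/365.25 = 9.00 | 9 | 7/15 = 47% |
| W52 | 365 × 12/365.25 = 11.99 | 12 | 8/15 = 53% |
| Month 18 | 549 × 12/365.25 = 18.04 | 15 | none after W52 |

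The 6-, 9- and 12-month landmarks are 182.63, 273.94 and 365.25 days, against nominal scans at 183, 274 and 365 on the SAP's count. Each lies within half a day.

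**4. Size, under an assumption**

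True against reported rate (%), for exponential time to progression, no censoring, uniform ±7-day windows, and DoR from a W12 response:

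| Landmark | DoR, median 6 | DoR, median 12 | PFS, median 6 | PFS, median 12 |
|---|---|---|---|---|
| 3 | 70.7 / 96.4 | 84.1 / 98.1 | 70.7 / 74.7 | 84.1 / 86.3 |
| 6 | 50.0 / 66.5 | 70.7 / 81.5 | 50.0 / 62.5 | 70.7 / 78.8 |
| 9 | 35.4 / 47.0 | 59.5 / 68.6 | 35.4 / 43.6 | 59.5 / 65.8 |
| 12 | 25.0 / 34.5 | 50.0 / 58.8 | 25.0 / 30.2 | 50.0 / 54.7 |
| 15 | 17.7 / 32.9 | 42.0 / 57.3 | 17.7 / 25.3 | 42.0 / 50.1 |

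**5. Where later landmarks would sit**

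The PFS windows at W26, W39 and W52 close at 6.24, 9.23 and 12.22 months. For DoR the next two windows close at 3.71 and 6.70 months after a W12 response, and at 106 × 12/365.25 = 3.48 and 197 × 12/365.25 = 6.47 after a W26 response. So 4 and 7 months clear both groups.

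With a 12-month median and nominal dates:
- PFS at 6.5, 9.5 and 12.5 months overstates by about 2.0, 1.7 and 1.4 points.
- DoR at 4 and 7 months overstates by about 3.5 and 3.0 points for W12 responders.
- For W26 responders it overstates by 84.0 − 79.4 = 4.6 and 70.7 − 66.7 = 4.0 points, against 100 − 84.1 = 15.9 and 84.0 − 70.7 = 13.3 at 3 and 6 months.

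Later DoR times do not work for everyone. At 10 months a W26 responder's last scan is at 6.01, which with a 9-month median gives 63% reported against 46% true.

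**The case against.** Dating progression at the assessment is conventional and overstates time to progression at any landmark. The times follow the protocol's own nominal language: section 14.2 pairs 9 and 15 months after dosing with 6 and 12 months of response follow-up. The SAP also gives medians, quartiles, a PFS plot and listings of derived efficacy data. It is an abbreviated plan for a terminated study that SAP 2.4 describes as no longer powered, and nothing is tested on these rates. Those points stand and limit the weight of the concern. They do not explain why DoR landmarks should sit just before the scans when a small shift avoids it.

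Stronger readings are tempting but go beyond the documents:
- A reader might infer that most PFS landmarks describe the previous scan. The 3-month one follows its scan in 93% of patients, and the 6-, 9- and 12-month ones are close to even.
- A reader might apply 88% to 91% to all responders. SAP 3.7.1.1 and 3.7.2.1 allow a response or CR first reached at any time, and for W26 responders the share is 53% to 60%. That matters most for DoCR.
- A reader might say that no scan lies near 12 months of DoR. For W26 responders one falls at 12.06 months.
- A reader might conclude that the rates cannot be compared with other trials. The documents give no other trial's scan schedule or landmarks.

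**Conclusion.** The concern holds, strongly for DoR and DoCR and partly for PFS. For week-12 responders the 3-month DoR rate is near 100% apart from deaths and unscheduled scans, and the 12- and 15-month rates both mainly reflect the Month 12 scan. For week-26 responders the effect is smaller. The 6-, 9- and 12-month PFS rates depend on which side of the visit window a scan happens to fall. The 15-month PFS rate adds no imaging beyond Month 12.

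The direction is overstated durability. The order of scans and landmarks needs only the schedule; the percentage shares also assume uniform, on-window scans. SAP 3.3 anticipates out-of-window assessments during COVID-19. The point sizes rest on an exponential distribution whose median the documents do not give: about 26 to 14 points at 3-month DoR for medians of 6 to 12 months in week-12 responders, and about 13 to 8 points at 6-month PFS. The analysis is descriptive, and the primary ORR is unaffected.

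**What to change.** **SAP 3.7.4.1.1 (PFS).** Keep 3 months. Move the 6-, 9- and 12-month landmarks past the close of the scan window, for example to 6.5, 9.5 and 12.5 months. Drop the 15-month rate or label it as status at the Month 12 scan.

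**SAP 3.7.3.2 (DoR and DoCR).** Replace 3 and 6 months with times after the next scan window, for example 4 and 7 months, which improve the estimate for both week-12 and week-26 responders. For later times, report response status by scheduled scan visit. Otherwise footnote that the 9-, 12- and 15-month rates carry forward the last scan, and that which scan this is depends on when response was first seen.

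**Cost.** SAP wording and the list of Kaplan-Meier times, with no new data. The downside is non-round landmark times and slightly less favourable rates.

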3.7.4 Secondary Endpoint: Progression-free survival (PFS)

3.7.4.1 Definition

PFS is defined as the interval from Betalutin administration and date of:

- Relapse (new or enlarged lesions after CR).
- Progression (new or enlarged lesions after PR or SD).
- Death from any cause.

Documented disease progression is defined as a Relapse (after CR) or progression (after PR or SD) and is indicated at the earliest date when the response assessment is given as progressive disease (PD). Death from any cause includes deaths occurring before the first post-baseline tumour assessment. If death occurs after two or more missed tumour assessments the participant should be censored (see below). PFS for participants meeting the events definition will be derived as follows:

$$\text{Progression-free survival time (months)} = ([\text{earliest of (First date of documented disease progression or death)} - \text{date of Betalutin administration}] + 1) * 12 / 365.25.$$

If none of the above events are observed PFS will be censored as follows:

- Incomplete/no baseline tumour IRC assessments: censor at date of Betalutin administration (study day 1).
- No documented disease progression: censor at date of last tumour IRC assessment where progression was not shown.

- Death or progression after two or more missed tumour assessments: censor at date of last tumour assessment where progression was not shown.

PFS for censored participants will be derived as:

$$\text{Progression-free survival time (months)} = ([\text{Date of censoring} - \text{date of Betalutin administration}] + 1) * 12 / 365.25$$

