12.1 Timing of Assessments and Imaging Modalities

12.1.1 Contrast Enhanced CT Examination

A baseline contrast-enhanced CT scan must be performed within 4 weeks prior to first rituximab infusion. [Table 6-5](#), [Table 6-7](#) and [Table 6-8](#), shows the frequency of subsequent contrast-enhanced CT scans per patient for follow-up.

A CT volume scan re-constructed **in up to 5 mm slides** with use of intravenously injected contrast agent will be performed per examination. The target lesions will be selected and measured at baseline, and followed at each efficacy assessment. The longest perpendicular diameters (major and minor axis) will be recorded in the eCRF.

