12.1.3 PET/CT Examination

The term ‘PET/CT imaging’ refers to PET imaging - which is typically undertaken on a combined PET/CT scanner.

PET/CT imaging will be done at baseline, 3 (Week 12) and 6 months after Betalutin administration for all patients. Baseline imaging must be performed within 4 weeks prior to administration of rituximab infusion. At these timepoints, both a PET scan and a separate contrast-enhanced CT scan (or MRI for those patients allergic to contrast) are to be undertaken. The same combined machine can be used if the CT scanner is a diagnostic quality CT scanner. At subsequent timepoints (Month 9 onwards), only a contrast-enhanced CT scan (or MRI) is required.

Standard institutional guidelines will be followed. The patient must have fasted for 6 hours prior to PET/CT imaging, water is allowed. For patients with known hyperglycaemia or diabetes, the blood glucose level must be < 11 mmol/L before injection of ¹⁸Fluorodeoxyglucose (FDG). Anti-diabetic drugs cannot be taken on the day of PET/CT examination.

PET/CT examination will be performed by a commercial combined PET/CT scanner. All scans should be performed on the same camera. PET/CT imaging will be performed about 60 to 70 minutes after intravenous administration of 5 to 10 mCi (185 to 370 MBq) of FDG. Same activity +/- 20% and time window must be used in the subsequent PET scans.

PET/CT scans will be done before contrast enhanced CT (or MRI for patients unable to receive contrast) when both modalities are to be done on the same day.

All measurements of uptake will be based on standardised uptake (SUV) values. Lesions <15 mm in short axis with abnormal activity: focal, above the surrounding background, above average liver SUV.

Guidelines for baseline CT examination:

- 1) Target lesions on the CT scans do not need to match those evaluated on the PET scan.
- 2) Target nodes should be chosen according to applicable Cheson criteria, see [Section 12.2](#).
- 3) Approximately 6 target nodes should be selected; there must be at least one target node.
- 4) The largest target nodes should be selected.
- 5) Nodes should be from different body regions if possible.
- 6) Mediastinal and retroperitoneal nodes should be included as target nodes if involved.
- 7) A measurable node must have a longest diameter (Ldi) greater than 1.5 cm.
- 8) A measurable extranodal lesion should have an Ldi greater than 1.0 cm.

Guidelines for baseline PET examination:

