14.1.7 Analysis of Efficacy Data

Tumour response will be reported as follows in individual patients:

- CR
- PR
- SD
- PD
- NE

In Part A and Part C: Response rate will be presented as a point estimate of the proportion of responders along with the 95 % exact confidence interval of response rate.

In Part B randomised period: The ORR will be compared between dosing regimens using the Fisher's Exact test, and the difference in response rates and the corresponding 95% exact CI will be presented. ORR estimates and 95% exact CI for each dosing regimen will also be presented.

In Part B Single-arm 40/15 part: – The primary efficacy analysis on ORR (based on independent assessment) will be performed by testing whether the ORR is less than or equal to 30% against the alternative hypothesis that ORR is greater than 20% at overall two-sided 5% level of significance, i.e.,

$H_0: p = 0.3$ vs. $H_a: p \neq 0.3$

In addition, the secondary efficacy analysis on CRR (based on independent assessment) will be performed by testing whether the CRR is less than or equal to 8% against the alternative hypothesis that ORR is greater than 8% at overall two-sided 5% level of significance, i.e.,

H0: $p = 0.08$ vs. Ha: $p \neq 0.08$

Responders are defined as having CR and PR according to definition in [Section 12.3](#).

Time to event endpoints will be analysed using standard Kaplan-Meier techniques. The estimate of the median survival curve will be calculated along with the associated 95% confidence intervals (when applicable). The efficacy endpoints are:

Overall Response Rate (ORR)

ORR, defined as the proportion of patients who achieve a CR or PR assessed with the use of standard criteria for lymphoma (1). The ORR will be assessed at 3 months image evaluation.

Best ORR will also be evaluated, taking the best response achieved independent of time point for image evaluation.

Complete Response Rate (CRR)

CRR, defined as the proportion of patients who achieve a CR assessed with the use of standard criteria for lymphoma (1). The CRR will be calculated based on complete responses achieved at any timepoint.

Progression-free survival (PFS)

PFS is defined as the interval from Betalutin administration and date of:

- Relapse (new or enlarged lesions after CR).
- Progression (new or enlarged lesions after PR or SD).
- Death from any cause.

If none of the above events are observed, PFS will be censored at the date of the last adequate tumour assessment

Duration of response (DoR)

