3.6.5.2 Rituximab

Participants are pre-dosed with 375 mg/m² rituximab once on Day -14. The actual rituximab dose administered (mg) and the actual dose standardised by BSA (mg/m²), as well as weight and BSA at rituximab infusion, will be summarised.

$$\text{Rituximab dose administered (mg/m}^2\text{)} = \text{Rituximab dose (mg)/BSA (m}^2\text{)}$$

Details relating to administration of rituximab will be listed separately.

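### The PFS censoring rules date a patient with no post-baseline scan and no counted event before treatment, and the progression definition conflicts with its own dating clause for PD at the first scan

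*SAP*

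**What the plan says.** SAP 3.7.4.1 counts PFS from the day of Betalutin (study Day 1) to relapse, progression or death. It has three censoring rules for patients without an event:

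- Baseline problem: "Incomplete/no baseline tumour IRC assessments: censor at date of Betalutin administration (study day 1".
- No progression seen: "No documented disease progression: censor at date of last tumour IRC assessment where progression was not shown".
- Death or progression after at least two missed scans: censor at the last scan that did not show progression.

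The same section states that a death before the first post-baseline scan is an event, unless the missed-scan rule applies.

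On scan timing, Protocol 12.1.1 says "A baseline contrast-enhanced CT scan must be performed within 4 weeks prior to first rituximab" infusion, and Protocol 12.1.3 says "Baseline imaging must be performed within 4 weeks prior to administration of rituximab infusion". SAP 3.6.5.2 gives "rituximab once on Day -14". The baseline scan therefore always precedes Betalutin.

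On the event itself, Protocol 14.1.7 lists "Progression (new or enlarged lesions after PR or SD") beside relapse after CR and death, and the SAP repeats that list. The SAP then adds "Documented disease progression is defined as a Relapse (after CR) or progression (after PR or SD"). The same sentence goes on to place progression at the earliest date on which the response is recorded as PD.

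**The concern.** None of the three censoring rules asks for a post-baseline assessment, and none sets Day 1 as the earliest censoring date. The SAP treats the baseline scan as an IRC assessment, both in the first censoring rule and in its Introduction, which describes IRC-evaluated baseline scans. A patient scanned at baseline and never again therefore has a last IRC assessment that lies before the PFS clock starts.

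Such patients are foreseeable. The Efficacy Analysis set (SAP 3.2.2) requires Betalutin at one of two dose levels, not a post-baseline scan. For ORR the SAP provides for missing assessments through its NE and ND categories (3.7.1.1 and 3.7.1.2). For PFS it does not.

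The progression definition is a separate fault. A patient whose first post-baseline scan shows PD has had no on-study CR, PR or SD. The defining words leave that patient out, and the dating words bring the patient in. A rule that decides who has an event should not depend on which half of a sentence the programmer follows.

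**Working it through.** **Plan's own figure.** Neither document states a PFS figure to reproduce. As a unit check, study day 92 gives 92 × 12 / 365.25 = 3.02 months, which agrees with SAP 2.1.1, where 12 weeks, 3 months and 92 days are equated.

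**Inputs**
- Censored PFS in months = (censoring date − Betalutin date + 1) × 12 / 365.25 (SAP 3.7.4.1).
- Baseline scan 0 to 28 days before rituximab (Protocol 12.1.1, 12.1.3).
- Rituximab 14 days before Betalutin (SAP 3.6.5.2), with ±2 days allowed on the Betalutin visit (SAP 2.1.1).
- Screening, and with it the validity of imaging, may be extended with sponsor approval; no length is given (Protocol 6.3).

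**Time assigned when the censoring date is the baseline scan**

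| Scan before Betalutin | Calculation | PFS (months) |
|---|---|---|
| 12 days (rituximab day, Betalutin 2 days early) | (−12 + 1) × 12 / 365.25 | −0.36 |
| 14 days | (−14 + 1) × 12 / 365.25 | −0.43 |
| 28 days | (−28 + 1) × 12 / 365.25 | −0.89 |
| 42 days (28 + 14) | (−42 + 1) × 12 / 365.25 | −1.35 |
| 44 days (Betalutin 2 days late) | (−44 + 1) × 12 / 365.25 | −1.41 |
| 56 days (assumes a 2-week extension) | (−56 + 1) × 12 / 365.25 | −1.81 |

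Censoring at Day 1 instead gives (0 + 1) × 12 / 365.25 = 0.03 months.

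**Which patients without a post-baseline scan are affected**
1. No death: censored at the baseline scan, so negative.
2. Death after at least two missed scans (for example Months 3 and 6): the third rule also goes back to the baseline scan, so negative.
3. Death before two scans have been missed: an event with a positive time, so not affected.

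**Effect on the Kaplan-Meier curve.** A patient censored at 0.03 months is in no risk set at any later event time. A patient dropped for a negative time is in none either. Unless an event falls on Day 1 itself, the curve, quartiles and 3- to 15-month rates are the same. What changes is the listed time and the counts of patients analysed and censored that SAP 3.7.4.1.1 requires.

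**PD at the first scan.** By the defining words there is no documented progression, and the censoring rule leads back to the baseline scan. By the dating words there is an event at the first scan. At Week 12 (84 days, ±7) that is (84 + 1) × 12 / 365.25 = 2.79 months, with a range of 2.56 to 3.02.

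**The case against.** The strongest reply is that little or nothing changes numerically. The first gap moves no Kaplan-Meier estimate, and a shortfall in the number analysed would show against the Efficacy Analysis set. SAP 3.7 also lists derived efficacy variables for patients with IRC data, so a negative time could be seen. PFS is a descriptive secondary endpoint in a terminated study. All of this stands, and it limits the point to a wording correction. It does not make the written rule produce a valid value.

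A second reply is that a baseline scan carries no response category, so a dataset built from visit responses may contain no baseline record. That is possible. The censoring date would then be undefined instead of negative, which is the same gap with the same remedy.

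On PD at the first scan, the reply largely succeeds. The dating clause gives such a patient a progression date, the PFS formula uses the first such date, and the PD criteria in Protocol Table 12-1 require no earlier CR, PR or SD. The likely program counts these patients as events.

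A reader might still infer that primary progressors vanish and early PFS rises to nearly 100%. The comparison would use Part A's 10 of 57 follicular lymphoma patients with PD (17.5%, leaving 82.5%; Protocol Table 4-3). The documents do not support this as an expected effect. It needs the less likely reading. It also borrows from Part A, which pooled dose arms, did not require anti-CD20-refractory disease and used investigator assessment by other criteria. Table 4-3 does not say when PD occurred.

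Nor does the July 2022 review of 61 patients with baseline and 3-month scans (SAP Introduction) show that others lacked a scan. Some may simply not have reached Month 3.

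**Conclusion.** The censoring gap is real on the literal text. A patient with a baseline scan, no post-baseline IRC scan and no counted death gets a PFS time of about −0.4 to −1.4 months under the standard windows, and lower if screening was extended. The time is undefined if the IRC data hold no baseline record. The same applies to a death after at least two missed scans with no post-baseline scan. It would be wrong to say that every patient without a post-baseline scan is affected, because an earlier death is an event with a positive time.

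The consequence is invalid listed times and wrong counts of patients included and censored. It is not a distorted curve, provided no event falls on Day 1. The number of patients affected is not given and cannot be worked out from the documents.

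The progression definition contradicts itself for PD at the first scan. This is an ambiguity to settle before the analysis. It is not evidence that primary progressors will be left out or that PFS will be inflated.

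**What to change.** Make two wording changes in SAP 3.7.4.1:

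1. Widen the first censoring rule: *baseline IRC assessment incomplete or missing, or no post-baseline IRC assessment, and no death counted as an event: censor at study Day 1.* Add that no rule may give a censoring date before Day 1. This also covers a death after at least two missed scans with no post-baseline scan.
2. Replace the event definition: *the first post-baseline IRC assessment of PD, whatever the earlier response, or death from any cause, subject to the existing missed-assessment rule.*

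The cost is the SAP wording and about two lines of program, with no new data. No protocol amendment is needed: Protocol 14.1.5 lets the SAP record changes to the planned analyses, and SAP 3.10 is the place to note this one.
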